1.0 Hypothesis and Objectives

1.1 Specific hypotheses:

- 1.1.1 Low serum 25(OH)D will be associated with increased treatment-related morbidity.
- 1.1.2 Repletion of 25(OH)D will be associated with an increase towards normal of serum leptin levels.
- 1.1.3 VDR *FokI* SNP polymorphism will be associated with lower circulating levels of 25(OH)D.

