3.0 Study Design

This study will contain 2 cohorts, those with normal serum 25(OH)D and those with low serum 25(OH)D at enrollment. The study will take place in women with ovarian, primary peritoneal, and fallopian tube cancer, subsequently referred to as ovarian cancer in this document due to the overlap in disease and treatment.

Patients who have given written consent to enroll in the study will have a serum 25(OH)D drawn in a gold-topped tube (1 to 5mL volume) at time of enrollment and prior to initiation of treatment for their cancer. Serum 25(OH)D levels will be analyzed per laboratory protocol in our University CLIA certified lab. Blood will also be drawn for analysis of serum leptin levels and VDR *FokI* SNP genotype. A purple-topped tube (7 to 10mL volume) and red-topped tube will be collected from prospective patients. The Stephenson Cancer Center Biospecimen Bank will process the red and purple-topped tube into plasma and Buffycoats, label them with a de-identified code and transfer them to [name] lab. The plasma

will be used to evaluate leptin by ELISA and the Buffycoats used to evaluate the *FokI* SNP using PCR. Retrospective serum specimens will be used to measure leptin.

Patients with low serum vitamin D levels, defined as <20 ng/mL, will be provided a supply of cholecalciferol (vitamin D3), 50,000 IU weekly for 8 weeks that will be dispensed in the Stephenson Cancer Center outpatient pharmacy in order to standardize therapy. They will then be provided with a prescription for 2,000 IU of cholecalciferol (vitamin D3) daily following completion of 8 weeks of therapy based on current Endocrine Society guidelines in agreement with U.S. Preventive Services Task Force recommendations [14]. Treatment with cholecalciferol will not impact initiation of treatment for ovarian cancer. Compliance with cholecalciferol repletion will be assessed with medication reconciliation at every gynecologic oncology visit.

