Vitamin D therapy will be stopped in any patient developing the above exclusion criteria of GFR <30, inability to tolerate oral medications, malabsorption syndrome, or primary hyperparathyroidism. In the unlikely event of evidence of vitamin D toxicity, treatment with vitamin D will be stopped. The Stephenson Cancer Center laboratory defines vitamin D toxicity as levels >100 ng/mL. Based on IOM literature, it would highly unlikely for individuals to experience vitamin D toxicity at the prescribed doses. Symptoms of vitamin D intoxication are caused by the resultant hypercalcemia and include anorexia, weight loss, polyuria, arrhythmias, fatigue, and soft tissue calcifications [20]. Patients experiencing these symptoms would receive testing for serum calcium and vitamin D. Vitamin D treatment would be stopped for any value indicative of toxicity.

Demographic, clinical, and disease characteristics and outcomes will be collected from all patients prospectively. The patient's treatment course information will also be collected prospectively, but will not be dictated by this study. Serum 25(OH)D and leptin levels will be collected again at the completion of primary therapy, 6 months after the completion of primary therapy, and at the time of disease recurrence. If disease recurrence occurs prior to 6 months after completion of primary therapy, this time point will be omitted. If disease recurrence does not occur prior to 1 year, serum 25(OH)D and leptin levels will be drawn at the time of the 1-year surveillance visit. If patients remain vitamin D deficient at any of these follow-up time points, they will be referred to an endocrinologist or primary care physician for further work-up and treatment of their vitamin D deficiency. Patients who are vitamin D deficient at completion of therapy but were not previously on supplement will be

IRB NUMBER: 7488
IRB APPROVAL DATE: 11/23/2021

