4.2 Inclusion Criteria (Prospective patients)

4.2.1 Patients must have a histologic diagnosis of ovarian, fallopian tube, or primary peritoneal carcinoma per pre-treatment biopsies by laparoscopy, or interventional radiology, paracentesis, or CT guided core biopsy. Histologic documentation of the original primary tumor is required via the pathology report.

4.2.2 Patients must have adequate:

4.2.2.1 Renal function: Glomerular Filtration Rate (GFR) ≥ 30 .

4.2.2.2 Gastrointestinal absorption: No underlying malabsorption syndrome (i.e. inflammatory bowel disease, celiac disease).

4.2.2.3 Ability to tolerate oral medication.

4.2.3 Patients taking vitamin D at the time of enrollment without a diagnosis of vitamin D deficiency.

4.2.4 Patients of childbearing potential must have a negative pregnancy test prior to the study entry and be practicing an effective form of contraception. If applicable, patients must discontinue breastfeeding prior to study entry.

4.2.5 Patients must have signed an IRB-approved informed consent and authorization permitting release of personal health information.

4.2.6 Patients must be at least 18 years old.

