4.3 Ineligible Patients

4.3.1 Patients with a known pre-existing diagnosis of vitamin D deficiency.

4.3.2 Patients with renal disease and a GFR < 30 .

4.3.3 Patients with primary hyperparathyroidism.

IRB NUMBER: 7488
IRB APPROVAL DATE: 11/23/2021

4.3.4 Patients with other invasive malignancies, with the exception of nonmelanoma skin cancer. Patients with concomitant endometrial cancer diagnosed at the time of their ovarian cancer are allowed to participate if the endometrial cancer is FIGO stage IB or less.

4.3.10 Patients of childbearing potential, not practicing adequate contraception, patients who are pregnant, or patients who are breastfeeding are not eligible for this trial.

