6.1 Patient Enrollment

When a suitable candidate has been obtained for protocol entry, the following steps should be taken:

6.1.1 An IRB-approved informed consent form and authorization permitting the release of personal health information must be signed by the patient or guardian. Current FDA, NCI and institutional regulations concerning informed consent will be followed.

6.1.2 All eligibility requirements indicated in Section 4.0 must be satisfied.

IRB NUMBER: 7488
IRB APPROVAL DATE: 11/23/2021

6.1.3 A completed, signed and dated, Patient Registration form should be filled out by the clinical study site (OU) and placed in the regulatory binder

6.1.4 Upon receipt of the signed and dated form from the clinical trials office at OU SCC, the clinical study site will enter the patient's name and study number in their Enrollment Log to verify the patient's entry into the study and additional study procedures may commence.

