12.0 Statistical Methods

Upon analysis, patients will be divided into two groups: Vitamin D Deficient Women and Vitamin D Normal Women.

IRB NUMBER: 7488
IRB APPROVAL DATE: 11/23/2021

Outcomes to be analyzed include differences in demographics, clinical, and tumor characteristics between groups, and differences in treatment-related morbidity or mortality between groups, including completion of treatment and treatment delays, and survival. Both 30-day postoperative surgical morbidity and chemotherapy-related morbidity will be assessed. The ability to normalize 25(OH)D levels with oral supplementation in the vitamin D deficient group will be evaluated.

Descriptive statistics will be used to summarize the demographic and clinical characteristics of patients. Chi-square and t-tests will be used to make comparisons between groups. Survival will be estimated with Kaplan-Meier curves and Cox proportional hazards regression. The anticipated enrollment is 100 patients based on estimated new diagnoses of ovarian cancer treated in the Division of Gynecologic Oncology annually at the Stephenson Cancer Center. Based on the previously mentioned unpublished data, we presume that at least 25 of the prospectively enrolled patients will be vitamin D deficient. All of the vitamin D deficient women will be repleted with oral vitamin D. We will compare outcomes between these patients and 75 vitamin D deficient ovarian cancer patients from previous years (these will include patients from the above-mentioned previous retrospective review as well as other patients with banked blood samples) using logistic regression. We will control for age, stage, and histology. With 25 prospective patients and 75 retrospective patients we will have 80% power to detect differences of 32% in chemotherapy delay between ovarian patients who were not vitamin D deficient (33%) and who were vitamin D deficient (65%).

Additionally, the association between serum leptin and 25(OH)D levels will be compared among groups, including any change in leptin levels observed in the vitamin D supplementation group. Because there is a positive linear association between BMI and serum leptin levels, BMI will be corrected for during analysis for potential relationships between serum leptin and 25(OH)D.

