#### 7. Translation Analyses

1. The proportion of patients with VDR FokI SNP will be assessed. We will also compare levels of vitamin D at diagnosis, differences in treatment-related morbidity or mortality including completion of treatment, treatment delays, survival and response to vitamin D supplementation across 3 SNP allele groups (homozygous mutated, heterozygous mutated, homozygous wild type).

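### As written, the inclusion criteria require every patient to be already taking vitamin D; reword this as permission, then record baseline use and adjust the FokI comparison for it to gain precision

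*Protocol*

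**What the plan says.** Protocol 4.2 (prospective patients) and SAP 3b give the same third inclusion criterion: "Patients taking vitamin D at the time of enrollment without a diagnosis of vitamin D deficiency". It is a fragment, with no verb to say whether use is required or allowed. Protocol 6.1.2 governs how the list is applied: "All eligibility requirements indicated in Section 4.0 must be satisfied". The related exclusion, Protocol 4.3.1, reads "Patients with a known pre-existing diagnosis of vitamin D deficiency".

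Other parts of the plan describe a wider population. Protocol 4.1.1 and SAP 3a.1 take newly diagnosed, previously untreated women and say nothing of supplements. Protocol 12.0 and SAP 2b base the enrollment of 100 on the centre's estimated annual new diagnoses. Protocol 3.0 makes provision for some women without a supplement: "Patients who are vitamin D deficient at completion of therapy but were not previously on supplement will be" referred to primary care.

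Cohorts are set by the measured level: "This study will contain 2 cohorts, those with normal serum 25(OH)D and those with low serum 25(OH)D at enrollment". For the translational question the hypothesis is "VDR *FokI* SNP polymorphism will be associated with lower circulating levels of 25(OH)D", and SAP 7 says "We will also compare levels of vitamin D at diagnosis" across three genotype groups, with no covariate named. The leptin analysis corrects for BMI only. For the primary comparison the plan states "We will control for age, stage, and histology". Neither document names vitamin D use at enrollment as a variable to be recorded. Medication reconciliation appears only as a check on compliance with the study cholecalciferol.

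**The concern.** An eligibility rule is applied by coordinators and checked by auditors, who work from the text. Anyone applying 4.2.3 through 6.1.2 as written would turn away every woman not already taking vitamin D, or would record her enrollment as a deviation. That would narrow the population, reduce accrual and leave fewer deficient women for the repleted group. SAP 3 has the statisticians confirm before analysis that the SAP criteria match the current ones. Because the two documents agree, that check would pass and the fault would remain.

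The permissive reading leaves a smaller matter. Supplement users then enter both cohorts, and baseline 25(OH)D varies partly because some women take vitamin D. The FokI comparison uses baseline 25(OH)D as its outcome, so this variation is noise that a single recorded variable could remove.

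**Working it through.** **1. The passages side by side**

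| Place | What it implies about non-users |
|---|---|
| Protocol 4.2.3, SAP 3b.3, with Protocol 6.1.2 | Not eligible |
| Protocol 4.1.1, SAP 3a.1 | Eligible; no supplement condition |
| Protocol 12.0, SAP 2b (100 from annual new diagnoses) | Counted in the expected accrual |
| Protocol 3.0 (deficient at completion, no previous supplement) | Probably expected in the study, though the supplement meant there could be the study cholecalciferol |

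The first row cannot stand with the second and third. The fourth supports the permissive reading without settling it.

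**2. The plan's own power figure**

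Inputs from Protocol 12.0 and SAP 2b: 25 and 75 patients, delay rates of 33% and 65%. Two-sided alpha of 0.05 is assumed, as none is stated.

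- Pooled rate: (25 × 0.33 + 75 × 0.65)/100 = 0.57.
- Null SE: √[0.57 × 0.43 × (1/25 + 1/75)] = 0.1143.
- Alternative SE: √[0.33 × 0.67/25 + 0.65 × 0.35/75] = 0.1090.
- z = (0.32 − 1.96 × 0.1143)/0.1090 = 0.88, so power is 81.1%.

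The stated 80% reproduces. It does not depend on 4.2.3 if use is merely permitted.

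**3. What the literal rule would do (illustration)**

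Assume that only users can enroll, that the 25 deficient women fall in proportion to the share of users, and that the 75 controls are unchanged. The documents give no rate of use, so a range is shown.

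| Share of users | Deficient prospective patients | Power |
|---|---|---|
| 100% | 25 | 81% |
| 75% | 18.75 | 72% |
| 50% | 12.5 | 57% |
| 25% | 6.25 | 35% |

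**4. Precision in the FokI comparison under permission**

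Let u be the share of users, d the mean rise in 25(OH)D from use, and SD the spread within genotype among women with the same supplement status. If use is independent of genotype and its effect is additive, leaving it out multiplies the variance by 1 + u(1−u)(d/SD)². The same factor is the ratio of sample sizes for equal precision. All values of u and d are assumed.

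| u | d/SD | Factor | Standardized effect, 1/√factor |
|---|---|---|---|
| 0.2 | 0.5 | 1 + 0.16 × 0.25 = 1.04 | 0.98 (about 2% smaller) |
| 0.5 | 1.0 | 1 + 0.25 × 1 = 1.25 | 0.89 (about 11% smaller) |

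Adjusting is therefore worth about 4% to 25% more patients.

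**5. The same covariate in the leptin model**

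Here 25(OH)D is the exposure. If supplement use reaches leptin only through 25(OH)D, adjusting discards useful exposure variance: 0.04/1.04 = 4% to 0.25/1.25 = 20% on the same inputs. The standard error of the slope then rises by √1.04 to √1.25, about 2% to 12% (ignoring any overlap with BMI). If use also tracks health behaviour that affects leptin beyond BMI, adjusting removes bias instead. The documents do not say which applies.

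**The case against.** The strongest reply is that nobody would apply 4.2.3 literally. It is the one item in its list with no verb, 4.1.1 sets no such condition, and it reads naturally as the counterpart of 4.3.1: a known deficiency excludes, and taking vitamin D without that diagnosis does not. I accept that permission is the likely intent, so the power losses in step 3 illustrate the literal rule and do not forecast this trial. The reply does not remove the fault, because 6.1.2 makes every listed requirement binding and the SAP repeats the sentence.

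A second reply is that the FokI and leptin questions are not the primary objective and carry no power claim. That is so, and it limits the weight of the covariate. It does not argue against a covariate that costs almost nothing.

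A reader might infer more than the documents support:

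- **Confounding of FokI by supplement use.** That needs use to be associated with germline genotype. Nothing in the documents suggests it, and none is expected. The consequence is lost precision.
- **Low-level women hidden among the normal.** Cohorts follow the measured level. A woman who is at or above the threshold because she supplements does have that level, and the absence of therapy listed for that cohort refers to study therapy.
- **A collision between 4.2.3 and 4.3.1.** The two are complementary. Excluding women with a known diagnosis is a design choice.
- **An understated proportion deficient, to be corrected from a screening log.** The documents do not say how many women 4.3.1 removes. Those women would have no study 25(OH)D, and an earlier deficiency may since have been corrected, so a tally could not supply the corrected proportion.

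**Conclusion.** The eligibility text is wrong as written. Protocol 4.2.3 and SAP 3b.3, read with 6.1.2, require current vitamin D use and contradict both the population in 4.1.1 and the basis of the enrollment estimate. This conclusion rests on the text alone and needs no assumption.

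The analytic part is modest. Under permission, baseline use is an unrecorded source of variance in the FokI comparison, with a factor of about 1.04 to 1.25. That range depends on assumed user shares of 20% to 50%, assumed effects of 0.5 to 1 SD, additivity, and independence of use from genotype. For 25(OH)D and leptin, confounding is plausible but not shown, and routine adjustment could cost precision. The reproduced power of 81.1% stands once permission is explicit.

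**What to change.** 1. Reword Protocol 4.2.3 and SAP 3b.3 identically, for example: vitamin D use at enrollment is neither required for entry nor a bar to it, provided that there is no diagnosis of vitamin D deficiency. Check the result against 4.1.1, 4.3.1 and the referral sentence in 3.0, and say there which supplement is meant.
2. Add a screening field for vitamin D use at enrollment (yes or no, and amount), taken from the medication history.
3. In SAP 7, make the comparison of baseline 25(OH)D across the three genotypes a linear model with baseline use as a covariate, in the prospectively enrolled patients for whom the field will exist. Describe the purpose as precision.
4. In SAP 5a.2, keep the BMI-adjusted leptin model as planned and add a sensitivity analysis that also includes baseline use.

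The cost is one sentence in each document, one form field, one covariate and one extra model. Sample size and the power statement do not change. The only analytic risk is the possible loss of precision for leptin, and confining the covariate to a sensitivity analysis keeps that out of the planned result.

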4.3 Ineligible Patients

4.3.1 Patients with a known pre-existing diagnosis of vitamin D deficiency.

4.3.2 Patients with renal disease and a GFR < 30 .

4.3.3 Patients with primary hyperparathyroidism.

IRB NUMBER: 7488
IRB APPROVAL DATE: 11/23/2021

4.3.4 Patients with other invasive malignancies, with the exception of nonmelanoma skin cancer. Patients with concomitant endometrial cancer diagnosed at the time of their ovarian cancer are allowed to participate if the endometrial cancer is FIGO stage IB or less.

4.3.10 Patients of childbearing potential, not practicing adequate contraception, patients who are pregnant, or patients who are breastfeeding are not eligible for this trial.

4.4 Inclusion of Minorities

Potential subjects shall not be excluded from participating in this or any study solely on the basis of ethnic origin or socioeconomic status. Every attempt shall be made to enter all eligible patients into this protocol and therefore address the study objectives in a patient population representative of the entire ovarian, fallopian tube and peritoneal primary cancer population treated by participating institutions.

5.0 Study Modalities

5.1 Cholecalciferol (vitamin D3)

Refer to the pharmacologic information for cholecalciferol. See

[figure not shown]
http://online.lexi.com/lco/action/doc/retrieve/docid/patch_f/6606#pro for the most complete and current information on the following:

5.1.1 Formulations

- Cholecalciferol (Vitamin D3) 50,000 IU is supplied as an oral capsule. It is a vitamin D analog. Cholecalciferol is a provitamin (25(OH)D) with an active metabolite 1,25-dihydroxyvitamin D (calcitriol). The drug is initially hydroxylated hepatically and then converted into the active metabolite renally.

IRB NUMBER: 7488
IRB APPROVAL DATE: 11/23/2021

5.1.2 Storage

Unopened vials of cholecalciferol are stable for the life indicated on the package stored at 15°C to 30°C (59°F to 86°F).

Adverse Effects: Consult the package inserts for the most current and complete information. No adverse reactions currently listed in manufacturer's labeling. According to the IOM, vitamin D toxicosis is highly unlikely at the prescribed doses. Symptoms of vitamin D toxicosis are caused by the resultant hypercalcemia and include: anorexia, weight loss, polyuria, arrhythmias, fatigue, and soft tissue calcifications [15].

Consult the American Hospital Formulary Service Drug Information guide, Facts and Comparisons, or the package insert for additional information.

5.1.3 Preparation and dosing

The dosage of cholecalciferol is based on current Endocrine Society guidelines in agreement with U.S. Preventive Services Task Force recommendations [14].

5.1.4 Drug ordering and distribution

IRB NUMBER: 7488
IRB APPROVAL DATE: 11/23/2021

Cholecalciferol will be ordered by and distributed from the outpatient pharmacy at the Stephenson Cancer Center. Study drugs will be kept in a locked space, physically separated from standard clinic or office drug supplies.

5.1.5 Drug Accountability:

All study drug received, dispensed and returned must be accounted for in a Drug Accountability log, including patient number and initials, date study drug dispensed, amount dispensed, amount returned (if applicable) and amount remaining in stock. The institution must maintain an accurate inventory log of all study drug received and used. Pill counts at each patient visit will be utilized to document compliance with oral medication.

6.0 Study Procedures and Treatment Plan

All necessary site-specific regulatory documents, including the PI biographical sketch, IRB approval, and IRB approved informed consent, must have been submitted to the IRB and the Stephenson Cancer Center CTO prior to beginning patient enrollment. The University of Oklahoma will submit the necessary documents to obtain national clinical trial listing

6.1 Patient Enrollment

When a suitable candidate has been obtained for protocol entry, the following steps should be taken:

6.1.1 An IRB-approved informed consent form and authorization permitting the release of personal health information must be signed by the patient or guardian. Current FDA, NCI and institutional regulations concerning informed consent will be followed.

6.1.2 All eligibility requirements indicated in Section 4.0 must be satisfied.

IRB NUMBER: 7488
IRB APPROVAL DATE: 11/23/2021

6.1.3 A completed, signed and dated, Patient Registration form should be filled out by the clinical study site (OU) and placed in the regulatory binder

6.1.4 Upon receipt of the signed and dated form from the clinical trials office at OU SCC, the clinical study site will enter the patient's name and study number in their Enrollment Log to verify the patient's entry into the study and additional study procedures may commence.

6.2 Treatment Plan

6.2.1 Screening visits will be conducted within 21 days prior to study drug administration.

Patients will undergo baseline evaluations prior to dosing.

6.2.2 This study will evaluate the administration of cholecalciferol to vitamin D deficient patients with ovarian cancer in relation to ability to replete 25(OH)D levels, treatment-related morbidity, and serum leptin levels.

